The goals are to determine if WECAC significantly reduces real-time maximum insertion pain (RTMIP) in both genders, to identify baseline patient-and procedure characteristics that predict low RTMIP, and to assess impact of WECAC on secondary outcomes. An additional goal is to develop pilot data to assess the hypothesis that WECAC, by increasing proximal colon ADR, can reduce the occurrence of post colonoscopy colon cancer (interval cancer) particularly in the proximal colon. This long term objective in the unsedated Veterans will be facilitated by identifying the least painful insertion method.

Patients who are willing to participate will sign an informed consent before starting the colonoscopy procedure. Separate parallel randomization will be set up at each site, stratified by investigator and type of colonoscopy (screening or surveillance). All subjects will have been scheduled for unsedated colonoscopy as a result of lack of escort or personal preference.

This multi-site study is designed to enroll 256 participants in total. Up to 150 patients are anticipated to enroll from the VA Greater Los Angeles Healthcare System. The performance

Version: 8/2016 1

site at the WLAVA will be in building 500, 5 East Clinical Procedure Center. The other study sites include: Sacramento VAMC and Palo Alto/Livermore VAMC.

This study is expected to take up to 5 years to complete. The expected duration of the patient's participation in this study is 1 hour for the colonoscopy procedure.

II. Screening Procedure

Patients will have already been scheduled for the colonoscopy procedure as part of their standard care. The patient will have received instructions for the standard preparation of the unsedated colonoscopy along with a flyer identifying and explaining the research study. The flyer will instruct the patient to call either the PI or the Study Coordinator for more information on the study if he/she is interested in participating.

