Exclusion criteria. Decline to be randomized, unable to give consent or respond to questionnaires, history of colon surgery, active inflammatory bowel disease, lower gastrointestinal bleeding (except for occult blood or FIT positive in the context of colon cancer screening), therapeutic colonoscopy (e.g., hemostasis, removal of large polyp), proctosigmoidoscopy, bidirectional endoscopy, inadequate consumption of bowel preparation, known history of severe diverticulosis or diverticulitis, history of abdominal surgery previously requiring sedation for colonoscopy, current narcotic/anxiolytic medication use, prior unsuccessful experience with unsedated colonoscopy, emergent colonoscopy, evidence of colonic obstruction based on pre-colonoscopy clinical evaluation, current participation in other studies, medical condition that could increase the risk associated with colonoscopy (e.g., active cardiac or pulmonary disease or other serious disease), medical condition that would preclude a benefit from colonoscopic screening (e.g., cancer or any terminal illness), prosthetic heart valve, anticoagulant therapy, nonmedical problems (e.g., psychiatric disorders, excessive use of alcohol), need for special precautions in performing colonoscopy (e.g. antibiotic prophylaxis), and request of on demand sedation.

Primary outcome measure (for male and female subjects).

	_
Real time maximum insertion	_
pain (RTMIP) (unblinded) score	
(validation by correlation with	
recalled pain described below)	

Pain during insertion reported to the unblinded assisting nurse, visual analogue scale, VAS: 0=none, 10=most severe. The highest pain score will be tabulated for analysis. Timing of data collection will be at the discretion of the nurse to minimize bias by colonoscopist behavior.

Secondary outcome measures (for male and female subjects).

Proportion with no insertion pain Proportion report no pain during insertion of the colonoscope. Quality marker.

Insertion time	Time to cecum (clock display on monitor). Faster insertion is a quality marker
Proximal colon ADR	ADR from cecum to splenic flexure. Measure of high quality colonoscopy

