Bowel preparation. Standardized split dose minimizes differences in bowel preparation quality. Trained support staff will provide the instructions to minimize variations in patient compliance. Efforts will be made (e.g., telephone reminders by research coordinator) to encourage proper compliance. The most up-to-date purge preparation will be used. Standard instructions will be provided by the schedulers. There are variations in the bowel regimen at participating sites at present. The preparation will be standardized during the start-up period. Veterans with diabetes, chronic constipation, or known history of poor bowel preparation will be asked to refrain from solid food intake for an extra day before colonoscopy.

Patient blinding. An air filled surrounding results in unblinding of the cap (rim around the tip). Several measures will be used to blind the patients. 1. The patients will not be informed of the technique (with or without cap), and what the cap at the tip looks like. 2. The colonoscope will be set up in the absence of the patient. 2. Before the start, a small towel will cover the eyes of the patients, and care will be taken not to

uncover the eyes when the patient is moved. Upon confirmation of arrival to the water-filled cecum (passing ileocecal valve, viewing the appendix opening and touching the cecal floor, or intubation of the terminal ileum), the patient will be asked to guess which technique has been used. If the correct guesses are <60%, adequate blinding during insertion will be assumed (3,4). As an accepted benefit of unsedated colonoscopy, the patient can observe and ask questions during the withdrawal phase. Air will be used to distend the lumen for inspection, and biopsy or polypectomy during withdrawal in all patients.

Adjunct maneuvers. These will include loop reduction, patient position change and abdominal compression. They will be employed in the order as listed to minimize assistant hand/wrist injury. Loop reduction will be applied whenever insertion is not associated with advancement of the tip of the colonoscope in the lumen. Position change will be employed whenever the tip of the colonoscope fails to advance despite loop reduction. Abdominal compression will be employed when both of the above fail to permit advancement of the colonoscope. The number of times application of these maneuvers is employed will be recorded for analysis.

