Timeline. A 6 month startup is anticipated to put all procedures in place (e.g. hire/train part-time coordinators, obtain local committee approval, prepare mailed material for patients. 51 months will be devoted to recruitment of subjects and performance of scheduled unsedated colonoscopy using WE or WECAC. The last three months will be devoted to data analysis and preparation of reports.

Flow Chart Based on CONSORT Guideline

(d) Description of base population and groups to be studied.

Base Population. Patients without escorts or with a personal preference for no sedation will be given a standard description (Table 3) of the scheduled unsedated option by the research coordinator (15). Veterans who accept the option will receive standardized verbal and written description of the RCT. Those interested in participation will be given a description of the study and consent form will be mailed for review. Prior to the start of colonoscopy, any further questions will be addressed. The patients will be informed that the endoscopist will use maneuvers (e.g., loop reduction, removal of colonic luminal content, position change, abdominal compression) to minimize insertion pain. These will be recorded by the assistant. Topical lidocaine (2%) will be applied to the anal canal to minimize purge or hemorrhoid-related anal discomfort. All subjects will be informed that the colon will likely react to the presence of the colonsocope to "push it back out". This translates into a sensation of an urge to have a bowel movement. The reaction is normal and natural. More severe pain will be reported to the colonoscopist who will employ maneuvers to minimize the pain. During the examination if implemented maneuvers fail to keep pain at a tolerable level, insertion will be halted. Enrolled patients will sign informed consent before start of colonoscopy to agree to be randomized, to allow the colonoscopy examination be recorded for analysis, to respond to questionnaires before, immediately after and at 24 hours, weekly thereafter until 30 days after colonoscopy. Subjects who fail cecal intubation due to pain have the option to reschedule for a repeat colonoscopy under sedation (with usual escort requirement).

(e) Justification of endpoints, procedures and links between questions, data, and endpoints.

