Primary outcome. Patient with insertion pain that cannot be brought to a tolerable level by colonoscopist implemented maneuvers will be considered failure of cecal intubation and the insertion will be discontinued. The pain level at the time of discontinuation will be noted for analysis.

Standardized validated instruments.

Proportion with no insertion pain, insertion time, proximal colon ADR (secondary outcomes in males) have been defined above; demographic data, co-morbidities, prior history and additional procedure based and patient level parameters will be analyzed as covariables (Tables 9 and 10).

Table 9: Demographic variables, co-morbidities and prior history				
Age	In years		Hemorrhoids	0=no, 1=yes
Gender	Male, female		Chronic pain treatments	0=no, 1=yes

Education	Elementary, high, college, graduate	Substance abuse	0=no, 1=yes
Ethnicity	White, Black, Hispanic, Asian, other	Prior abdominal surgery	0=no, 1=Yes (type)
BMI	Weight/height ²	Prior sedation colonoscopy	0=no, 1=yes
Indication	Screening, surveillance, diagnostic, pain	Prior unsedated colonoscopy	0=no, 1=yes

Table 10: Additional procedure based and patient level covariates				
Recalled maximum insertion pain	Maximum pain during insertion reported to a blinded observer after			
score (blinded data)	colonoscopy before discharge, VAS: 0=none, 10=most severe. Correlation with RTMIP.			
Overall ADR - entire colon	Proportion of patients with at least one adenoma of any size.			
Right colon ADR	ADR from cecum to hepatic flexure			
Adequacy of patient blinding	Patient guesses which method is used (<60% correct=adequate).			
Successful cecal intubation	0=no, 1=yes			
Successful cecal ilitubation	Abdominal pain prior to start of colonoscopy: 0, none to 3, severe (recorded			
Current abdominal discomfort	before examination)			
Loop reduction maneuvers	Number of times used, recorded by nurse assistant			
Position change	Start with left lateral, change as needed to supine, right lateral, prone.			
Abdominal compression	0=no, 1=Yes (sigmoid, transverse, hepatic, right side)			
Need to change technique	0=no, 1=yes (to air insufflation)			
Water volumes (insertion) Volume of water (infused and suctioned) upon arrival to the cecum, eq				
	volumes confirm appropriate application of water exchange			
Water volumes (total)	Volume of water (infused and suctioned) at the end of colonoscopy			
	Documented during withdrawal (4=excellent, no residual stool; 3=good, small			

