Exploratory hypotheses. Co-variables affect patients' report of RTMIP. Patient-related factors include age, gender, ethnicity, education, BMI, indication for colonoscopy, current symptomatic hemorrhoids,

Dependent Variables	Variable	Analysis method		
Primary Outcome				
RTMIP	Continuous	Mixed effects regression, predict lower insertion pain, predictors-covariables		
Co-variables			Variable	Analysis method
Recalled maximum inse	Recalled maximum insertion pain score (blinded) [validates primary]			Correlate RTMIP
Body mass index (yes, no)			Continuous	
Age (<40 years) (yes, no); gender (male, female); ethnicity (White, Black, Hispanic, Asian, other) (yes, no); indication (Screening, surveillance, diagnostic); hemorrhoids (yes, no); chronic pain treatments (yes, no); substance abuse (yes, no); prior abdominal surgery (yes, no), sedation colonoscopy (yes, no), unsedated colonoscopy (yes, no), painful colonoscopy (yes, no); diverticulitis (yes, no); indication (abdominal pain) (yes, no); anticipation of pain (yes, no);  Exploratory variables			Binary	
Staff satisfaction (0=not satisfied to 10=very satisfied)			Continuous	
Adequacy of patient blinding (yes, no); Loop reduction maneuvers (yes, no); Position change (yes, no); Abdominal compression (yes, no); Need to change technique (yes, no); Failed (poor prep) (yes, no); Pain tolerance (patient reported) (0=low, 1=high); Reason for unsedated (no ride, personal preference, other) (yes, no); Previous endoscopy experience (0=not good, 1=good); Objective anxiety (0=none, 1=high) (by endoscopist before examination); overall adenoma detection - entire colon (yes, no);			Binary	

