chronic pain treatment, substance abuse, prior abdominal surgery, prior colonoscopy with or without sedation, current abdominal discomfort, expectation on day of colonoscopy, patient reported pain tolerance and subjective anxiety, objective anxiety assessed by colonoscopist, and reason for choice of no sedation. Procedure-related factors include technique of insertion, use of loop reduction maneuvers by the colonoscopist, change of patient position, application of abdominal compression by the assistant and insertion time, and length of colonoscope needed to reach the cecum. Examples: patients are more likely to report higher RTMIP amongst those with younger age, longer duration of insertion, lower expectation of painless insertion, female gender, low BMI, more frequent need for position change or abdominal compression. More patients will report lower RTMIP if there is low patient anxiety, good expectation of today's examination, no

prior abdominal surgery, colonoscopist use loop reduction maneuvers. The analysis of the exploratory outcomes will follow the same structure as the primary and secondary outcomes. To control for the multiplicity of exploratory outcomes we use the false-discovery rate (FDR) of Benjamini and Hochberg (67) rather than the traditional Bonferroni adjustment. The FDR assesses estimates the proportion of significant findings that are false positive results. The FDR method is less conservative and better preserves our ability to detect differences between groups.

Interim analysis. After 50% of subjects complete the protocol and data collection we will perform an inferential analysis of the primary endpoint as described in the statistical methods section. The only difference between the interim analysis of the primary endpoint and the final analysis will be the level of significance of the tests. If there is a significant treatment effect, this would communicated to the study Data and Safety Monitoring Board (DSMB) to consider early termination for efficacy.

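### Regressing RTMIP on loop reduction (yes/no) cannot test whether the maneuver lowers pain: the coefficient is biased upward and may reverse sign

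*SAP*

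**What the plan says.** One stated goal (Protocol, Introduction; repeated in Specific Objectives) is "to identify baseline patient-and procedure characteristics that predict low RTMIP".

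The SAP's Exploratory hypotheses turn this into directional examples. Features expected to go with lower RTMIP end with no "prior abdominal surgery, colonoscopist use loop reduction maneuvers". Features expected to go with higher RTMIP include "more frequent need for position change or abdominal compression" and longer insertion. The analysis table gives the method as "Mixed effects regression, predict lower insertion pain, predictors-covariables" and lists loop reduction, position change and abdominal compression as yes/no variables. Protocol Table 10 collects loop reduction as a count.

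Under Primary hypothesis, the SAP first fits each covariate with group, gender and a covariate-by-group interaction. It then places the significant covariates in one regression with group assignment. Random effects for site and for provider within site are added.

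The Protocol defines the outcome and the use of maneuvers as follows:

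- Primary outcome measure: "The highest pain score will be tabulated for analysis".
- Adjunct maneuvers: "Loop reduction will be applied whenever insertion is not associated with advancement of the tip of the colonoscope in the lumen". Position change follows if loop reduction fails, and compression follows if both fail.
- Base Population: "More severe pain will be reported to the colonoscopist who will employ maneuvers to minimize the pain". The same paragraph names loop reduction among the maneuvers.
- Justification of endpoints, for insertions that are stopped: "The pain level at the time of discontinuation will be noted for analysis".
- Table 8: frequent loop reduction is a component of both techniques.

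**The concern.** The predictor is partly a response to what the outcome measures. A patient whose scope advances freely and without pain has little reason to receive loop reduction; a patient with a difficult or painful insertion does. Comparing users with non-users is then largely a comparison of hard with easy insertions. Because RTMIP is a maximum, relief after the maneuver cannot lower a peak already recorded. Stopped insertions push the same way, since they are scored after the maneuvers have failed.

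Nothing in the planned model separates these directions. Group, gender, site and provider do not measure difficulty at the moment of use, and Table 10 lists no timing of maneuvers against pain scores. The false-discovery-rate step limits chance findings, but it does not correct bias.

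At stake is one stated exploratory hypothesis. The result could suggest that loop reduction does nothing or raises pain, although the Protocol's Background says it consistently reduced insertion pain. In addition, a maneuver variable found significant would enter the regression with group assignment. It is recorded after randomization and could take up part of the arm difference there.

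**Working it through.** The plan states no figure for this test, so there is none to reproduce.

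**1. Consistency of the stated directions.** By the Protocol's order, a patient who has position change or compression has already had loop reduction. The SAP treats the later steps as markers of difficulty (higher RTMIP) and the first step as protective (lower RTMIP). If need marks difficulty for the later steps, it does so for the first step as well.

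**2. Closed form.** Let tau be the true benefit in points, rho the correlation between the latent trigger for use and RTMIP, SD the standard deviation of RTMIP, and p the share of users. Then

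expected coefficient = -tau + rho x SD x G, with G = phi(c)/p + phi(c)/(1-p) and c the cut-point giving share p.

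- SD = 2.2 (SAP pilot, men on WE). Assume p = 0.5, so c = 0 and phi(c) = 0.399.
- G = 0.399/0.5 + 0.399/0.5 = 1.596, and SD x G = 3.51.
- Upward bias: 0.35, 0.70, 1.05 and 1.76 points at rho = 0.1, 0.2, 0.3 and 0.5.
- The sign reverses when rho exceeds tau/3.51, that is 0.14, 0.28 and 0.57 for tau = 0.5, 1 and 2.
- With SD = 3.7 (women on WECAC), SD x G = 5.90, and a 1-point benefit is reversed above rho = 1/5.90 = 0.17.

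**3. Simulation with the SAP's yes/no coding.** There were 230 patients (144 men + 86 women, the evaluable targets), six insertion segments and 300 runs per setting. RTMIP was the maximum of scores held within 0 to 10. The model was least squares on group, gender and loop reduction; it omitted the covariate-by-group interaction and the random effects. The benefit acts within segments, so even an unconfounded coefficient is smaller than the benefit. The rho = 0 rows are the proper comparison. Here rho links a patient's latent pain level to the latent tendency not to advance. Entries are the mean coefficient and the share of runs with a positive (wrong) sign.

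| Trigger | Routine users | Benefit 0.5 | Benefit 1 | Benefit 2 |
|---|---|---|---|---|
| Non-advancement, rho 0 | none | -0.12 (31%) | -0.22 (19%) | -0.26 (10%) |
| Non-advancement, rho 0.3 | none | +0.50 (99%) | +0.44 (97%) | +0.40 (96%) |
| Non-advancement, rho 0.6 | none | +1.16 (100%) | +1.09 (100%) | +1.05 (100%) |
| Non-advancement, rho 0 | 30% | -0.32 (7%) | -0.58 (0%) | -1.00 (0%) |
| Non-advancement, rho 0.3 | 30% | +0.03 (57%) | -0.22 (13%) | -0.63 (0%) |
| Non-advancement, rho 0.6 | 30% | +0.45 (98%) | +0.19 (85%) | -0.25 (14%) |
| Pain | none | +2.89 (100%) | +2.90 (100%) | +2.89 (100%) |
| Pain | 30% | +0.90 (100%) | +0.61 (99%) | +0.13 (70%) |

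These rows record pain before relief. Recording it after relief, without carry-over to later segments, changed the non-advancement means by at most 0.05. It lowered the pain-trigger means to +2.40, +2.05 and +1.67 with no routine use, and to +0.76, +0.38 and -0.23 with 30%.

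**4. Reading.** Against the matching rho = 0 row with 30% routine users and a 1-point benefit, the shift is -0.22 - (-0.58) = +0.36 at rho 0.3 and 0.19 - (-0.58) = +0.77 at rho 0.6. With no routine users it is 0.44 - (-0.22) = +0.66 and 1.09 - (-0.22) = +1.31. The shift is always upward, but whether it crosses zero depends on the setting. Under the non-advancement trigger, confounding by difficulty does nearly all the work; the retained peak matters mainly under the pain trigger.

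**The case against.** The strongest reply is that reversal is not established. The specific rule for loop reduction is non-advancement, not pain, and Table 8 makes frequent loop reduction part of both techniques without a condition. Some use is therefore routine. With 30% routine users the mean coefficient kept the right sign in several settings. This stands. A reader might infer that the coefficient must come out positive, with very small p-values that survive the false-discovery-rate step. The documents do not support that: it needs purely pain-triggered use, or purely reactive use with a fairly strong link to pain. If loop reduction is nearly universal, the likelier outcome is an uninformative yes/no variable. A slope per use would likewise not describe the analysis table, which codes yes/no.

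A trigger unrelated to pain is nevertheless hard to square with the Protocol, whose Background calls sigmoid looping a cause of pain and links technically difficult insertion to more pain.

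Second, the SAP predicts higher RTMIP with position change, compression and longer insertion. The bias pushes those coefficients in the predicted direction, so no wrong sign is shown for them. That also stands; they remain markers of difficulty and not evidence of effect.

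Third, the goal is worded as prediction and the hypotheses are exploratory. This limits the consequence. It does not rescue an example that credits the colonoscopist's use of a maneuver with lower pain.

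**Conclusion.** The point holds in limited form. As planned, the loop-reduction coefficient is biased upward and cannot test the SAP's prediction of lower RTMIP; it may reverse sign even if the maneuver works. For assumed benefits of 0.5 to 2 points, mean coefficients ranged from about -0.6 to +2.9 points wherever the trigger tracked pain. The most negative value, -1.0, arose only with a trigger unrelated to pain, 30% routine users and a 2-point benefit. The true benefit, the strength of the trigger-pain link and the share of routine use are assumptions, because the documents give none of them. The qualitative conclusion rests on the outcome definition and the written triggers, not on any one setting.

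A reader might also infer that the trial's main result is compromised. It is not: the primary two-sample comparison of arms does not use the maneuver variables. Only the exploratory predictor analysis and the secondary adjusted regression are exposed.

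**What to change.** In the SAP's Exploratory hypotheses and its analysis table:

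- Delete the directional prediction for loop reduction.
- Report loop reduction, position change and abdominal compression as outcomes by arm: counts or proportions, the difference and its confidence interval.
- Describe any association of a maneuver, or of insertion time, with RTMIP as a non-causal marker of difficulty.
- Base the inferential model for predicting low RTMIP on variables recorded before insertion.

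Under Primary hypothesis, state that these post-randomization variables are not carried into the multiple regression with group assignment.

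The cost is wording and a descriptive table. The maneuvers are already recorded, and the cover page lists the trial as completed, so the change can be made in analysis and reporting without new data. The real loss is that the procedure-factor part of the exploratory objective becomes descriptive. That part is stated in both the abbreviated and the detailed Protocol, so the narrowing should be declared openly in the report.
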